Women are at higher risk of drug-induced TdP, in part due to testosterone production in males beginning at puberty. However, estrogen lengthens the QTc interval,⁴ which is shorter during the luteal phase of the menstrual cycle (when serum progesterone is highest) than in the follicular phase.⁵ Progesterone has an androgen structure similar to testosterone and is a testosterone precursor in testicular Leydig cells. In women with long QT syndrome (LQTS), TdP risk is low during pregnancy, but increases post-partum, when serum progesterone declines.⁶ Progesterone-induced shortening of ventricular action potential duration (APD) is reversed by progesterone receptor inhibition.⁷ In a transgenic rabbit LQTS type 2 model, progesterone reduced the incidence of spontaneous polymorphic ventricular tachycardia (PVT) or sudden cardiac death (SCD) and ventricular early afterdepolarizations.⁸ Older age is a risk factor for TdP in women, likely due to the decline in serum progesterone concentrations after menopause. Overall, data indicate that progesterone shortens ventricular repolarization and protects against drug-induced ventricular APD lengthening and arrhythmias.

We conducted a prospective, double-blind “proof-of concept” study, assessing the effect of oral progesterone on drug-induced QT interval lengthening in young women.¹⁰ We randomized n=19 healthy women 21-40 years of age to receive 7 days of therapy with oral progesterone 400 mg once daily or matching placebo. After a washout period, subjects were crossed over to the alternate therapy. Women were studied during the menses phase, to minimize the influence of endogenous sex hormones. Following 7 days of treatment, subjects received intravenous ibutilide 0.003 mg/kg and QTc interval

response was determined. Pre-ibutilide QTc intervals were significantly shorter during the progesterone phase. In addition, both the mean maximum QTc interval and maximum % change in QTc interval from pre-ibutilide value were significantly shorter during the progesterone phase.¹⁰ On the basis of this “proof-of-concept” study, we now propose to investigate the effects of oral progesterone administration on drug-induced QTc interval lengthening in a target population of interest: postmenopausal women, who have low serum progesterone concentrations.

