Serum ibutilide concentrations will be performed in the CPAC Laboratory^{9,20} and serum estradiol and progesterone concentrations will be performed in the IU Health Pathology Laboratory.²¹ In each of the two groups of subjects (postmenopausal women and premenopausal women), peak serum ibutilide concentrations and area under the serum ibutilide concentration:time curves from 0-1 hours (AUC₀₋₁) be compared across the groups to assure no differences that could influence QT intervals. QT intervals will be measured by an investigator with vast training and experience in QT interval measurement, and who will be blinded to subjects' assigned treatment groups. Area under the effect (AUEC; effect = QT interval) vs time curves from 0-1 hour following ibutilide administration (AUEC_{0-1.17}, accounting for the 10-minute ibutilide infusion) and from 0-8 hours following ibutilide (AUEC_{0-8.17}), indices of QTc interval exposure, will be calculated using the linear trapezoidal rule.

In summary, this study will take a total of 15 days to complete, excluding the washout periods. The total study period will take place over a minimum of 15 days. Each subject will need to complete 3 visits, and take a medication for 7 days prior to visits 2 and 3. The first visit involves no drug administration, but simply involves a 1 hour stay in the ICRC and includes a screening visit. Then subjects will begin self-administration of study medications for 7 days. Visit 2 begins the day after the 7th day of medication administration. During visit 2, the subjects will undergo an approximate 10 hour stay in the ICRC. After a minimum of a 14 day washout period, subjects will self-administer study medications for 7 days. Visit 3 begins on the day after the 7th day of medication administration. During visit 3, the subjects will undergo an approximate 10 hour stay in the ICRC.

Genetic testing:

Subjects have the option of consenting to a single 10ml blood draw at the time of another scheduled blood draw in the study. This sample will be used for genetic testing. Subjects will be genotyped for polymorphisms for an array of relevant genes, including those that encode for cytochrome P (CYP) 450 3A5, which is a major contributor to progesterone metabolism;3 other CYP enzymes contributing to progesterone metabolism, including 2C19, 2C9, and 3A4;4 progesterone receptors;5 estrogen receptors; potassium current, including hERG and KCNQ1; and calcium current.

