8.0 Statistical Considerations

Statistical analysis will be performed separately for the two subject populations:

- Postmenopausal women (progesterone vs placebo)
- Premenopausal women (progesterone vs placebo)

QT intervals will be corrected for heart rate using two correction methods, the Fridericia (QT_F) and Framingham (QT_{Fra}) methods.

Study Endpoints: Comparison of progesterone and placebo phases for: 1) Baseline (pre-ibutilide) maximum QT_F & QT_{Fra} 2) Ibutilide effect on maximum QT_F & QT_{Fra}, 3) Ibutilide effect on maximum % change in QT_F & QT_{Fra}, and 4) Ibutilide effect on AUEC_{0-1.17} and AUEC_{0-8.17}. Endpoints will be correlated with progesterone concentrations. 5)

Statistical analyses: Means (standard deviations) or medians (interquartile range) will be presented for continuous variables. Distribution normality will be assessed using the Kolmogorov-Smirnov test. Paired t-test (if normality holds) or signed-rank test (if normality does not hold) will be used to compare outcome measures between the two treatment phases; 95% confidence intervals will be calculated. SAS 9.4 (Cary, NC) will be

used. Correlations between the primary endpoints and serum progesterone concentrations will be performed using Pearson's correlation coefficient.

Anticipated Outcomes: During the progesterone phase, the following outcome measures will be significantly lower than vs placebo: 1) Pre-ibutilide QT_F and QT_{Fra}; 2) Post-ibutilide maximum QT_F and QT_{Fra}; 3) AUEC 1 hour and 8 hours after ibutilide; 4) Post-ibutilide % change in maximum QT_F and QT_{Fra}, 5) J-T_{peak} and T_{peak-T_{end}}.

Sample Size Calculation: In this 2-way crossover study, at a two-sided α level of 0.05 and a power of 0.80, a sample size of 20 subjects in the postmenopausal population and n=20 subjects in the premenopausal population will be sufficient to detect a difference in maximum QT_F and QT_{Fra} of 15 ms, assuming a QT_F and QT_{Fra} interval prolongation of 24±12 ms associated with ibutilide in the absence of progesterone.

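### The AUECs, and possibly the powered maximum QTc, are not measured from the pre-ibutilide value, so a shorter baseline on progesterone could be read as attenuation

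*Combined protocol and SAP*

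**What the plan says.** Section 2.0 states the hypotheses of Aims 1 and 3 as attenuation of the drug-induced QTc response, first in postmenopausal women and then in premenopausal women at ovulation.

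The endpoints meant to show this are set out in two places:

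- **AUECs (Section 5.0).** The integrand is the interval: "Area under the effect (AUEC; effect = QT interval) vs time curves from 0-1 hour following ibutilide administration". The same sentence calls the two areas "indices of QTc interval exposure, will be calculated using the linear trapezoidal rule". No baseline is subtracted, and the sentence moves between QT and QTc.
- **Maximum QTc (Section 8.0).** The sample size is called "sufficient to detect a difference in maximum QT_F and QT_{Fra} of 15 ms". The planning figure is an "interval prolongation of 24±12 ms associated with ibutilide in the absence of progesterone", which is a change. The Anticipated Outcomes list, after a lower pre-ibutilide QTc, "2) Post-ibutilide maximum QT_F and QT_{Fra}; 3) AUEC 1 hour and 8 hours after ibutilide", which reads as an absolute level.
- **Maximum % change (Section 8.0).** "Ibutilide effect on maximum % change in QT_F & QT_{Fra" is the one endpoint written relative to a reference value, and Section 8.0 does not say what that value is.

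A paired t-test or signed-rank test "will be used to compare outcome measures between the two treatment phases", with no baseline term. Section 8.0 mentions primary endpoints but does not identify them.

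On the earlier crossover study in women aged 21–40 during menses, Section 1.0 reports: "Pre-ibutilide QTc intervals were significantly shorter during the progesterone phase". It does not give the size of that difference.

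**The concern.** An absolute post-ibutilide QTc is the pre-ibutilide QTc plus the response to ibutilide. If progesterone shortens the first part and leaves the second alone, the absolute maximum and both absolute AUECs still fall. Randomised order and blinding give no protection, because the shift is itself an effect of progesterone.

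The protocol expects this shift and makes it an endpoint of its own. A significant maximum QTc or AUEC, read alone, therefore cannot separate a shorter resting QTc from a smaller drug response, and only the second is the stated aim. Maximum % change could separate them, but the plan does not say which result decides if the endpoints disagree. That choice would then be made after the results are known.

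**Working it through.** **Inputs from Section 8.0.** 20 women per population, two-sided α 0.05, power 0.80, difference 15 ms, ibutilide prolongation 24 ± 12 ms. **From Section 5.0:** the ECG time grid and return of QTc to baseline in 2–6 h. The size of the shift and the SD of the within-woman difference are not given, so ranges are used.

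**1. The plan's own sample size.** With SD 12 and difference 15, the unpaired normal formula gives 2 × 12² × (1.96 + 0.84)² / 15² ≈ 10.0 per group. Ten per group (20 in all) has power 0.798, which matches the stated figure, although the design is paired. A paired t-test needs 8 women if the SD of the difference is 12 ms, and 13 if it is 12√2 = 17.0 ms (no within-woman correlation). It has 80% power at exactly n = 20 only if that SD is about 22.7 ms. These three SDs are used below. The last is back-solved, not documented.

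**2. Absolute maximum QTc with zero attenuation.** Chance of p < 0.05 in a paired t-test, n = 20, noncentral t with noncentrality shift × √20 / SD:

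| Baseline shift | SD 12 | SD 17.0 | SD 22.7 |
|---|---|---|---|
| 3 ms | 19% | 12% | 9% |
| 5 ms | 42% | 24% | 15% |
| 10 ms | 94% | 71% | 46% |

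On the change scale every cell would be 5%.

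**3. AUEC in ms·h.** Assume a linear rise to 24 ms over the 10-minute infusion and a linear return over 2–6 h, with the linear trapezoid on the protocol's grid.

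- Whole ibutilide effect: 26–74 in AUEC0–8.17 and 20–24 in AUEC0–1.17.
- A 5 ms baseline shift alone: 5 × 8.17 = 40.8 and 5 × 1.17 = 5.8.

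Over 8 hours, a 5 ms shift is therefore worth between about half (40.8/74) and one and a half times (40.8/26) the entire ibutilide effect.

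**4. AUEC simulation.** 4,000 crossovers of 20 women per scenario, zero attenuation, 5 ms shift, 4 h return, reading SD 6 ms. Visit SD and response SD were (6, 0), (6, 6), (6, 12), (10, 12) and (12, 12) ms. Absolute AUEC0–8.17 was significant in 22–64% of trials and absolute AUEC0–1.17 in 16–66%. The baseline-subtracted versions gave 4–6%.

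**5. Maximum % change.** With an assumed 400 ms baseline and a 24 ms response, a 10 ms shift moves it from 24/400 = 6.00% to 24/390 = 6.15%. It is almost unaffected, and what movement there is goes slightly against progesterone.

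**6. Power for attenuation, if the 15 ms is an absolute difference that includes a shift.**

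| Shift within the 15 ms | Left for attenuation | Power at n = 20 (SD 22.7 / 17.0 / 12) | n for 80% power (SD 12 / 17.0 / 22.7) |
|---|---|---|---|
| 5 ms | 10 ms | 46 / 71 / 94% | 14 / 25 / 43 |
| 10 ms | 5 ms | 15 / 24 / 42% | 48 / 93 / 164 |

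If the 15 ms is already a change and 12 ms is the SD of that change, paired power at n = 20 is at least 96% (SD of the difference 17.0 ms or less).

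**The case against.** The plan already lists pre-ibutilide QTc and maximum % change beside the absolute measures, and pre-ibutilide triplicate ECGs are taken at both visits. A wrong conclusion would require the investigators to set aside two prespecified endpoints that would expose it. The percentages above are rejection rates for one endpoint read alone, not the chance that the trial as a whole misleads. The Anticipated Outcomes are predictions, not a decision rule, and labelling the AUECs as exposure indices is fair. The wording of endpoint 2, an ibutilide effect, together with the 24 ms planning figure, can support a change-scale reading of maximum QTc. The power argument needs an absolute 15 ms that contains a shift, and its worst values use an SD with no source in the documents.

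Most of this stands as a limit on size. The sample-size part is conditional and secondary, and a shift of about 3 ms would matter little. Section 1.0 also reports a smaller maximum % change on progesterone in the earlier study, so attenuation may well be real here. None of it supplies the missing rule. The AUEC definition as written omits the baseline, the scale of the powered variable is unsettled, and nothing says that the attenuation claim rests on the endpoint able to test it. Absolute QTc may matter clinically, which is a reason to keep it as an exposure outcome but does not make it a test of attenuation.

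**Conclusion.** The concern holds and should be fixed. It is mainly a defect of interpretation, not a shortage of subjects. The AUEC part follows directly from the text. For maximum QTc, the absolute reading is the more natural one, but the text does not settle it. The size depends on the baseline shift, which the documents do not give for either population: at 5 ms the absolute endpoints would be significant in roughly 15–66% of trials with no attenuation, against a nominal 5%. These figures rest on the assumed shift, SDs and return profile shown above. n = 20 is adequate if the 15 ms is a change-scale difference with the ±12 ms as its SD. It may fall short of 80% power for attenuation if the 15 ms includes a baseline shift.

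**What to change.** **Section 8.0**

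- In each population, name one baseline-relative endpoint, with one named correction method, to carry the attenuation claim: maximum change in QTc, in ms, from the mean of the same visit's pre-ibutilide triplicate. The existing maximum % change would also serve if that reference value is stated.
- State that absolute maximum QTc and absolute AUEC are secondary total-exposure outcomes and are not read as evidence of attenuation.
- State whether the 15 ms is on the change scale, and give the assumed SD of the within-woman difference. If the 15 ms includes a baseline shift, restate the power for n = 20.

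**Section 5.0**

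- Compute both AUECs on change in QTc from that same baseline, and say QTc throughout.

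**Cost.** Wording in two sections and a restated sample-size basis; the ECGs needed are already collected. The baseline-relative endpoint carries the noise of one triplicate mean per phase, and the stated power may become less favourable. If the 15 ms is already a change, n = 20 need not move. The rule should be fixed before unblinding.

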3.0 Inclusion/Exclusion Criteria

Inclusion Criteria:

Specific Aims 1&2: Postmenopausal women, based on the following criteria:

- Age \geq 50 years **AND**
- No menstrual periods for \geq 365 days

Specific Aims 3&4: Premenopausal women, 21-40 years of age

Exclusion Criteria (apply to all specific aims):

- History of breast, uterine or ovarian cancer
- History of hysterectomy and/or ovariectomy
- Weight $>$ 135 kg
- Serum K^+ $<$ 3.6 mEq/L;
- Serum Mg^{2+} $<$ 1.8 mg/dL;
- Hematocrit $<$ 26%;
- Hepatic transaminases $>$ 3x upper limit of normal;
- Baseline Bazett's-corrected QT interval $>$ 450 ms
- Taking hormone replacement therapy
- Diagnosis of heart failure
- Symptoms associated with heart failure:
 - Pitting edema $>$ 2+
 - Crackles or rales on lung auscultation
 - S3 or S4 heart sounds
 - Unable to climb \geq 2 flights of stairs without becoming short of breath
- Current ECG rhythm of atrial fibrillation or other tachyarrhythmia

- Family or personal history of long-QT syndrome or sudden cardiac death not associated with acute myocardial infarction
- Concomitant use of any QTc interval-prolonging drug.
- Permanently paced ventricular rhythm
- Pregnancy
- Using any hormonal contraceptives (oral contraceptives, hormone-secreting intrauterine devices (IUDs), hormonal implants)
- Peanut allergy
- We will exclude subjects who are currently taking medications that induce or are moderate or strong inhibitors CYP 2B6/3A4/3A5 metabolism :

Carbamazepine (tegretol)	Phenytoin	Phenobarbital	Plioglitazone (actos)	Refabutin
Rifampin	St Johns Wort	Troglitazone (rezulin)		

Clopidogrel (Plavix)	Ticlopidine	Voriconazole	HIV antiviral meds	Verapamil
Diltiazem	Suboxone	Aprepitant		

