5.0 Study Procedures

This study will be performed using a crossover design. Each subject will act as her own control. Subjects will be randomized to the order that they receive either the study medication or the placebo. A random number generator will be used to determine the order of randomization. Subjects will be randomized during their first visit to the Indiana Clinical Research Center (ICRC) after informed consent has been obtained.

This study will be conducted at the ICRC. All subjects will undergo a screening visit (visit 1) that will include obtaining of a 12-lead ECG, performance of a history and physical examination, obtaining height and weight, and bloodwork. Using a two-way crossover design, each subject will be studied **two times**, serving as her own control. During each phase, subjects will receive a single IV dose of ibutilide 0.003 mg/kg, which will be administered by an ICRC nurse.^{9,10} Each subject will **take oral progesterone 400 mg orally once daily in the evening**, or use **matching placebo** daily in the evening for 7 days. The crossover order will be randomized. The study design is summarized below in Figure 1:

[figure not shown]

Figure 1. Study design

This study will be conducted with 3 visits: visit one is a screening visit; visits 2 and 3 includes 7 days of medication self-administration followed by a 10 hour ICRC visit. There will be a minimum 14-day washout period between visits 2 and 3. In premenopausal women, during each phase, subjects will be studied during the ovulation phase of the menstrual cycle. The ovulation phase is selected for this study rather than the luteal phase because, while serum estradiol is similar in the two phases, the natural progesterone:estradiol ratio is lower in the ovulation phase.⁹ In order to time the administration of ibutilide and measurement of on-drug QT intervals to the ovulation phase, premenopausal women with a typical 28-day menstrual cycle will begin taking their study medication on the 5th day of their menstrual period (see Figure 2). For women who typically have longer menstrual cycles (30-35 days), study drug therapy will be initiated on the 6th or 7th day of their menstrual periods (Figure 2).

[figure not shown]

Figure 2. Hormone fluctuation during the menstrual cycle.

Visit 1 (Screening visit):

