Subjects will be asked to come to the ICRC at IU Health University Hospital. An investigator will review the procedures and risks of the study in detail and obtain written informed consent. After written informed consent is obtained, subjects will undergo a screening history and physical examination performed by an investigator. Three 12-lead ECGs one minute apart (QTc will be averaged across ECGs to determine eligibility), height, weight and blood work will be obtained at this time to determine serum potassium, magnesium, liver enzymes, hematocrit. Premenopausal women will undergo a urine human chorionic gonadotropin (HCG) test to rule out pregnancy.

Once laboratory results are obtained and the physical is completed and the subject has met inclusion criteria and has no exclusion criteria, the subject will be enrolled in the study. If the subject meets any exclusion criteria, they will not be allowed to proceed in the study. This process will take approximately 1 hour.

Immediately following the screening history and physical examination, subjects will be randomly assigned to two groups:

Group A: (n= 20 subjects)

Each subject will take two placebo capsules once daily in the evening for 7 days.

Group B: (n= 20 subjects)

Each subject will take oral progesterone 400 mg orally once daily (two x 200 mg capsules) in the evening for 7 days.

Subjects will be sent home with one week's supply of the study medication to which they are initially randomized and a medication diary with which to keep track of when they take the medication, any adverse effects they may experience, and any changes in their own

concurrent medications. They will receive written and verbal instructions about the study medication and dates will be established for Visit 2.

Visit 2:

Prior to the visit subjects will be NPO and remain NPO until 4 hours after the end of the ibutilide dosing. Subjects may drink non-caloric drinks during this period such as coffee, tea, diet soda, water ect. If the serum potassium concentration is low as defined previously in the protocol, then the subject may have orange juice or a banana as previously defined in the protocol.^{26,27,28}

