Two indwelling intravenous catheters will be placed, one in each arm. Blood will be drawn to determine serum progesterone, estradiol, and pre-ibutilide potassium and ibutilide concentrations. Blood for a serum ibutilide concentration will be obtained prior to administration of ibutilide (and therefore will have no detectable ibutilide) will be obtained because sometimes the assay lab uses a "blank" serum sample in validation of the assay. If any subjects are found to have hypokalemia as defined in the exclusion criteria:

- They will be offered a glass of orange juice and/or a banana. After consuming the potassium-containing food, another blood sample for serum potassium concentration will be obtained and sent to the laboratory OR
- The subject's visit will be rescheduled

If the subject chooses to drink a glass of orange juice and/or eat a banana, and the follow-up serum potassium concentration is still < 3.6 mEq/L, the subject's visit will be rescheduled, or the subject can withdraw from the study, whichever of those options they prefer

Pre-menopausal women will also undergo a urine HCG test to rule out pregnancy prior to ibutilide administration. Pre-menopausal women with a positive HCG urine test will be withdrawn from the study.

All subjects will receive a single intravenous (IV) dose of ibutilide 0.003 mg/kg, which will be administered by an ICRC nurse. The ibutilide dose will be calculated based on the subject's weight during their screening visit. However, subjects will be weighed upon arrival at the CRC; if their weight is > 10% different than the weight recorded during their screening visit, the weight recorded upon arrival for this visit will be used to calculate the ibutilide dose. An MD ([name] or his designee) will be notified regarding the scheduled time of ibutilide administration.

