Continuous ECG monitoring will be initiated 30 minutes prior to ibutilide and will continue until the post-ibutilide Bazett's-corrected QT interval is < 450 ms, which generally occurs within 2 hours following administration of this low, subtherapeutic dose of ibutilide. Three 12 lead ECGs approximately one minute apart (three ECGs within a total of 5 minutes) will be selected for QT interval measurement before (time 0) and after ibutilide at: at 5 minutes during infusion, end of infusion, 5, 10, 15, 20, 30 and 45 minutes and 1, 2, 4, 6, and 8 hours. Blood (6 mL) for determination of ibutilide concentrations will be obtained from the indwelling catheter in the arm contralateral to that into which ibutilide infused was approximately the following times (within 5 minutes of the times listed) 5 minutes during infusion, at the end of infusion, and 5, 10, 15, 20, 30 & 45 minutes, and 1, 2, 4, 6, and 8 hours following end of infusion. An 8-hour data collection and monitoring period is sufficient, as QT_c intervals return to baseline within 2-6 hours.^{9,10}

In addition, blood will be drawn to determine serum progesterone, estradiol, and potassium concentrations at the same time as the time 0 ibutilide concentration is drawn. If the subjects is found to have hypokalemia as defined in the exclusion criteria, then they will be withdrawn from the study.

At 3-7 days following the study visit, subjects will be called/texted or emailed based on preference to assess for any potential adverse events related to study medications or procedures.

Following visit 3, subjects' participation in the study will be complete.

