The risks associated with this investigation will be minimized by the administration of a subtherapeutic dose of ibutilide (0.003 mg/kg, approximately 20% of the lowest therapeutic dose, approximately 10% of the highest therapeutic dose). In addition, risks will be minimized, in large part, by the exclusion criteria employed, which will allow us to exclude patients that are at risk for experiencing excessive QT interval prolongation associated with a subtherapeutic dose of ibutilide. Subjects with specific risk factors for TdP will be excluded – these risk factors include hypokalemia, hypomagnesemia, pretreatment QTc interval > 450 ms, liver disease, NYHA class IV HF, LVEF < 20%, history of TdP, and taking other QT interval-prolonging drugs. During the day on which ibutilide will be administered, patients will be maintained on continuous ECG telemetry monitors until the post-ibutilide Bazett's-corrected QT interval is < 450 ms, which generally occurs within 2 hours following administration of this low, subtherapeutic dose of ibutilide. Ibutilide will be administered in the ICRC which is housed within University Hospital and has full medical services if needed in the case of an emergency. There is a cardiac arrest (code) cart in the CRC that includes magnesium sulfate. A physician investigator (or his designee) will be notified regarding the planned time of administration of ibutilide administration. Subjects will not be discharged from the ICRC if they have a QTc interval of > 450ms after treatment. They will be monitored until the QTc interval is below 450ms. This study has a DSMB to periodically monitor the safety and any adverse events which may occur.

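### Magnesium has an exclusion limit but is measured only at screening; adding it to the blood already drawn before each ibutilide dose would be a cheap safety improvement

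*Combined protocol and SAP*

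**What the plan says.** Section 3.0 lists "Serum Mg^{2+} $<$ 1.8 mg/dL" among the exclusion criteria for all aims, next to a potassium limit of 3.6 mEq/L. Section 6.0 says the exclusions do much of the work of limiting ibutilide risk and names both electrolytes: "these risk factors include hypokalemia, hypomagnesemia".

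At Visit 1, section 5.0 says "blood work will be obtained at this time to determine serum potassium, magnesium, liver enzymes, hematocrit". No ibutilide is given at that visit.

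At Visit 2, and again in the same words at Visit 3, the pre-dose sample is described as "Blood will be drawn to determine serum progesterone, estradiol, and pre-ibutilide potassium and ibutilide concentrations". A woman with low potassium may take a potassium-containing food and be retested, or be rescheduled. If "the follow-up serum potassium concentration is still < 3.6 mEq/L", she is rescheduled or may withdraw. The Visit 3 text later repeats the list: "blood will be drawn to determine serum progesterone, estradiol, and potassium concentrations at the same time as the time 0 ibutilide concentration is drawn". It then gives a different consequence: "If the subjects is found to have hypokalemia as defined in the exclusion criteria, then they will be withdrawn from the study". Magnesium appears in none of these pre-dose lists. The only other mention of magnesium is the magnesium sulfate on the code cart (section 6.0), which is a treatment and not a check.

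**The concern.** Ibutilide is given only at Visits 2 and 3, so those are the days on which electrolytes need to be in range. By redrawing potassium with an action rule, the plan accepts that a screening electrolyte value can go out of date. Section 6.0 lists magnesium beside potassium, yet the plan relies on its screening value throughout and gives no reason for treating the two differently.

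Section 7.0 lets the investigator withdraw a woman whose eligibility changes, but a fall in magnesium below the limit would not be seen, because no planned test looks for it. What is at stake is volunteer safety on the dosing day. The endpoint analysis in section 8.0 is not in question.

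**Working it through.** **Number of doses.** Section 4.0 plans 20 postmenopausal and 20 premenopausal women: 20 + 20 = 40. This agrees with the section 6.0 safety board meetings at 1/4, 1/2 and 3/4 of subjects (10, 20 and 30). Section 5.0 gives one ibutilide dose in each of two phases, so planned doses = 40 x 2 = 80, if all women complete. The documents do not state the figure of 80; it follows from these two inputs.

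**Which doses have a same-day check.**

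| | Visit 1 (no ibutilide) | Visit 2 (ibutilide) | Visit 3 (ibutilide) |
|---|---|---|---|
| Potassium | measured | measured, with action rule | measured, with action rule |
| Magnesium | measured | not listed | not listed |

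Planned same-day potassium: 40 + 40 = 80 of 80 doses. Planned same-day magnesium: 0 of 80.

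**Age of the screening magnesium.** Take Visit 1 as day 0, with study drug starting that evening (or the next). The seventh dose falls on day 6 (or 7), and section 5.0 places Visit 2 on the following day.

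- Visit 2: day 7 (or 8).
- Visit 3: section 5.0 says "There will be a minimum 14-day washout period between visits 2 and 3" and describes Visits 2 and 3 as each including their 7 days of medication. The washout therefore comes before the second dosing week, as the Visit 2 text and the closing summary of section 5.0 also say. Age = 7 + 14 + 7 = 28 days (or 8 + 14 + 7 = 29).
- Visit 3, premenopausal women: dosing is tied to the day of the cycle, so Visit 3 falls at least one cycle after Visit 2. Age = 7 + 28 = 35 days for a 28-day cycle and 7 + 35 = 42 days for a 35-day cycle, assuming regular cycles and Visit 1 on the first dosing day.

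All of these are minimum ages. The washout is stated only as a minimum and no screening-to-dose window is given, so the plan sets no upper limit.

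**Background risk.** The largest possible dose is 135 kg x 0.003 mg/kg = 0.405 mg. Section 6.0 gives 0.5 mg as the lowest dose linked to TdP in published work. The Appendix total at 0.003 mg/kg is 58 + 31 + 42 + 20 = 151 records with no TdP.

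**What cannot be computed.** The documents give no rate at which a woman who passes screening later falls below 1.8 mg/dL. No number of affected doses can be derived.

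**The case against.** The strongest reply is that nothing in the plan is wrong. The statement in section 6.0 can be read as describing exclusion at entry, and sections 3.0 and 5.0 deliver that. This stands. A reader might infer that the plan contradicts itself, but the text does not support that.

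The plan also has partial cover. Section 6.0 provides phone calls during dosing, the diary in section 5.0 records adverse effects and medication changes, and section 7.0 allows withdrawal when a change in medical condition raises risk, which needs no laboratory value. ECG monitoring continues until QTc is below 450 ms, and magnesium sulfate is at hand. These measures lower the stakes, but none of them measures magnesium.

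Other stronger readings should be set aside:

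- Section 6.0 lists nausea and vomiting with progesterone, and a reader might infer that treatment lowers magnesium. The documents do not say so. Section 6.0 calls these effects minimal, and section 1.0 reports that in the investigators' own trial only fatigue/malaise was significantly more frequent than on placebo.
- A reader might split the 151 records by sex to argue that the safety record in women is thin. The Appendix does not allow a clean split: the 58-person row counts persons who received three doses, the other rows count doses, and one row does not state sex.
- A reader might count the 14 days from clinic day to clinic day and put Visit 3 at day 21. The section 5.0 definition of the visits rules this out.
- A reader might assume a magnesium hold is neutral because magnesium is not an endpoint. That is not established: if progesterone did affect magnesium, holds would fall unevenly between phases.

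**Conclusion.** The gap is real and minor. A sponsor-named risk factor with its own exclusion limit has no planned check on any of the 80 dosing occasions, against 80 of 80 for potassium. The value relied on is at least 7-8 days old at the first dose and at least 28-29 days old at the second (about 35-42 days in premenopausal women). These figures assume that all 40 women complete, that study drug starts on the day of screening or the day after, and, for the premenopausal range, regular cycles with dosing started on the day of screening.

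A reader might infer that volunteers face a material risk of TdP. The documents do not support that: there are 0 of 151 records at this dose, the maximum dose is below 0.5 mg, and no event is tied to low magnesium. The case for change is that the safeguard costs little and follows the plan's own handling of potassium.

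**What to change.** Add magnesium to the tests run on the blood already drawn for pre-dose potassium at Visits 2 and 3. If it is below 1.8 mg/dL, do not give ibutilide that day and reschedule. Write the same consequence for both visits, since the Visit 3 potassium text offers rescheduling in one place and withdrawal in another. Make the decision blinded to phase, and report the number of holds by phase and population, because they could be unbalanced. State whether a postmenopausal woman who is rescheduled extends or repeats her 7-day course.

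The cost is a short amendment and 80 assays, assuming the laboratory can report magnesium along with the pre-dose potassium. The downside is an occasional rescheduled visit. For a premenopausal woman this means another cycle and a repeat 7-day course, which matters with only 20 women per population and a paired analysis. The Visit 1 screening results would show how often values fall below 1.8 mg/dL and give a rough guide to how many holds to expect.
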